- If a subject has a pre-existing episodic condition (eg, asthma, epilepsy) any occurrence of an episode should only be captured as an AE if the episodes become more frequent, serious or severe in nature, that is, the investigator or subinvestigator should ensure that the AE term recorded captures the change in the condition from Baseline (eg “worsening of...”).
- If a subject has a degenerative concurrent medical condition (eg, cataracts, rheumatoid arthritis), worsening of the condition should only be captured as an AE if occurring to a greater extent to that which would be expected. Again, the investigator or subinvestigator should ensure that the AE term recorded captures the change in the condition (eg, “worsening of ...”).

Worsening of AEs:

- If the subject experiences a worsening or complication of an AE after starting administration of the study drug, or if a sign or a symptom appears secondarily due to an AE, the worsening or complication should be recorded appropriately as a new AE. The investigator or subinvestigator should ensure that the AE term recorded captures the change in the condition (eg, “worsening of...”).
- If the subject experiences a worsening or complication of an AE after any change in the study drug, or if a sign or a symptom appears secondarily due to an AE, the worsening or complication should be recorded as a new AE. The investigator or subinvestigator should ensure that the AE term recorded captures the change in the condition (eg, “worsening of...”).

Changes in severity of AEs:

- If the subject experiences changes in severity of an AE that are not related to starting the study drug or changing in the dose or regimen, the event should be captured once with the maximum severity recorded.

Preplanned surgeries or procedures:

- Preplanned procedures (surgeries or therapies) that were scheduled prior to signing of informed consent are not considered AEs. However, if a preplanned procedure is performed early (eg, as an emergency) due to a worsening of the pre-existing condition, the worsening of the condition should be captured appropriately as an AE. Complications resulting from any planned surgery should be reported as AEs.

Elective surgeries or procedures:

- Elective procedures performed where there is no change in the subject's medical condition should not be recorded as AEs, but should be documented in the subject's source documents. Complications resulting from an elective surgery should be reported as AEs.

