10.2.1.2 AE Reporting

At each study visit, the investigator or subinvestigator will assess whether any subjective AEs have occurred. A neutral question, such as “How have you been feeling since your last visit?” may be asked. Subjects may report AEs occurring at any other time during the study. Subjects experiencing a serious AE that occurs prior to the first exposure to study drug must be monitored until the symptoms subside and any clinically relevant changes in laboratory values have returned to baseline or there is a satisfactory explanation for the change. Non-serious AEs that occur prior to the first exposure to study drug, related or unrelated to the study procedure, need not to be followed-up for the purposes of the protocol.

All subjects experiencing AEs after the first exposure to study drug, whether considered associated with the use of the study drug or not, must be monitored until the symptoms subside and any clinically relevant changes in laboratory values have returned to baseline or until there is a satisfactory explanation for the changes observed. All AEs will be documented in the AE page of the eCRF, whether or not the investigator or subinvestigator concludes that the event is related to the drug treatment. The following information will be documented for each event:

1. Event term.
2. Start and end date.
3. Pattern.
4. Severity.
5. Investigator’s opinion of the causality between the event and administration of study drug(s).

6. Investigator's opinion of the causality to study procedure(s), including the details of the suspected procedure.
7. Action taken with study treatment (not applicable for the AE that occurred before the study drug administration).
8. Outcome of event.
9. Seriousness.
10. After administration of study drug.
11. Treatment emergent.

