13.1.5 Safety Analysis

[Primary endpoints]

AEs, anthropometric (weight, height and BMI) measurements, laboratory tests, resting 12-lead ECG, and vital signs (office standing blood pressure, office sitting pulse rate, office standing pulse rate, and home sitting blood pressure)

[Analytical methods]

The following analyses will be conducted with the safety analysis set.

1) AEs (Treatment-emergent AEs)

A treatment-emergent AE (TEAE) is defined as any AE occurring after the start of TAK-536 administration of the Treatment Period.

The incidence of TEAEs listed below will be analyzed. TEAEs will be coded using the Medical Dictionary for Regulatory Activities (MedDRA). The frequency distribution will be provided using the system organ class (SOC) and preferred term (PT) using MedDRA as follows:

- TEAEs
 - Drug-related TEAEs
 - Severity of TEAEs
 - Severity of drug-related TEAEs
 - TEAEs leading to study drug discontinuation
 - Serious TEAEs
 - TEAEs over time
- 2) Anthropometric (weight, height and BMI) measurements, laboratory tests, resting 12-lead ECG, and vital signs (office standing blood pressure, office sitting pulse rate, office standing pulse rate, and home sitting blood pressure)

For continuous variables, the observed values and the changes from the end of the Run-in Period (Week 0) will be summarized for each time point. In addition, individual figures of the observed values will be provided.

For categorical values, shift tables of the data before and after administration will be provided.

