7.0 METHODS OF ANALYSIS AND PRESENTATION

7.1 General Principles

7.1.1 Study Definitions

- Day of last observation/test or contact, whichever comes later: Last date of SDTM.SV
- Treatment-emergent adverse event (TEAE): Any AE occurring after the first study drug administration for the Treatment Period
- Pretreatment event (PTE): Any AE occurring after obtaining informed consent but before the first study drug administration for the Run-in Period
- Adverse event during the Run-in Period: For subjects who enter the Treatment Period, any
 AE occurring after the first study drug administration for the Run-in Period until the first
 study drug administration for the Treatment Period. For subjects who do not enter the
 Treatment Period, any AE occurring after the first study drug administration for the Run-in
 Period
- Summary statistics: Number of subjects, mean, standard deviation, maximum, minimum, and quartiles
- Duration of exposure to study drug for the Treatment Period: Date of the last study drug administration for the Treatment Period – Date of the first study drug administration for the Treatment Period + 1
- Study period after the study drug administration for the Treatment Period: Date of last observation/test or contact – Date of the first study drug administration for the Treatment Period + 1
- Compliance rate with the study drug for the Treatment Period: Total number of doses of study drug for the Treatment Period (Amount of study drug dispensed for the Treatment Period Amount of study drug returned for the Treatment Period) / Duration of exposure to study drug for the Treatment Period × 100 (rounded to 1 decimal place)
- Office trough sitting diastolic and systolic blood pressures on each measuring day: The mean of 3 values on a given measuring day (rounded to integers) is used as the representative value of that measuring day.

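### Protocol 10.1.2 has two overlapping rules for an AE that worsens, and one of them can keep an on-drug worsening of an earlier AE out of the TEAE tables

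*Protocol*

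**What the plan says.** - **Protocol 10.1.2, Worsening of AEs.** Two bullets, both driven by timing. The triggers are "If the subject experiences a worsening or complication of an AE after starting administration of the study drug" and "If the subject experiences a worsening or complication of an AE after any change in the study drug". The first bullet concludes that "the worsening or complication should be recorded appropriately as a new AE"; the second has the same effect. Neither sets a condition on cause.
- **Protocol 10.1.2, Changes in severity of AEs.** This rule is driven by relation. Where a child has "changes in severity of an AE that are not related to starting the study drug or changing in the dose or regimen", then "the event should be captured once with the maximum severity recorded".
- **Protocol 10.1.8.** An AE's start date is when its first signs or symptoms were noticed. Nothing resets it when severity rises within one record.
- **TEAE definition.** Protocol 13.1.5: "A treatment-emergent AE (TEAE) is defined as any AE occurring after the start of TAK-536 administration of the Treatment Period". SAP 7.1.1: "Any AE occurring after the first study drug administration for the Treatment Period". Neither has a clause for the worsening of an earlier AE.
- **Earlier events.** SAP 7.1.1 classes an AE between consent and the first Run-in dose as a pretreatment event, and one between that dose and the first Treatment Period dose as a Run-in AE. SAP 7.11.1.3 and 7.11.1.4 tabulate each class only as all events and serious events, by system organ class and preferred term.
- **TEAE displays.** The tables by intensity, relationship and discontinuation, and those for hypotension-related and renal events, are in SAP 7.11.1.1 and 7.11.1.2 and cover TEAEs only.

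**The concern.** The two rules in 10.1.2 overlap. A worsening that comes after TAK-536 is started, but is judged not related to starting it or to a dose change, satisfies both. One rule asks for a new record and the other for a single record, and no precedence is given.

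The choice would not matter if the TEAE definition picked up worsening by itself. It does not, so for an AE that began before the first TAK-536 dose the choice of rule decides whether the on-drug worsening is a TEAE at all.

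AEs are among the primary endpoints (protocol 5.2.1). The SAP tabulates all TEAEs separately from drug-related TEAEs, so the all-cause tables should not turn on a view of relatedness. The study has one arm, so no control group shares the loss.

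**Working it through.** No stated figure stands behind this point, so the check is a trace through the rules, followed by the size of one event.

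**Step 1. Example.** A mild AE starts in the Run-in Period, the child starts TAK-536, and the AE becomes severe at Week 10 with no recent dose change. The investigator judges the change unrelated to starting TAK-536.

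| | Worsening rule applied | Severity rule applied |
|---|---|---|
| Records | Original AE plus a new AE | One AE, severity raised to severe |
| Start date carrying the severe grade | Week 10 | Run-in |
| Class under SAP 7.1.1 | New record is a TEAE | Run-in AE |
| TEAE and intensity tables (SAP 7.11.1.1, 7.11.1.2) | Counted, as severe | Not counted |
| Hypotension or renal table, if the term is listed in the SAP appendix | Counted | Not counted |
| Run-in table (SAP 7.11.1.4) | Original AE, no intensity shown | The AE, no intensity shown; also in the serious table if serious |

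An AE that starts between consent and the first Run-in dose follows the same path, with SAP 7.11.1.3 in place of 7.11.1.4.

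**Step 2. Does another reading of relatedness remove the conflict?** Suppose the severity rule's condition is read as closeness in time rather than cause. A Week 10 worsening without a dose change would still count as unrelated and be captured once. The overlap remains.

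**Step 3. Size of one event.** Planned N is 50 (protocol 13.3), and TEAE percentages by term use the safety analysis set as denominator (SAP 7.11.1.2).

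- Full study, weight groups combined: 1/50 = 2.0 percentage points.
- Week 12 interim, about 25 children: 1/25 = 4.0 points. SAP 7.12 includes the intensity, hypotension and renal TEAE tables in that analysis.
- Display cut-off: SAP 7.11.1.2 item (12) lists non-serious TEAEs by preferred term at 2% or more. With exactly 50 children, one child (2.0%) just meets it.

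These are upper limits for a row, because a child with another TEAE in the same row is already counted. Rows by weight group have smaller denominators, so one child weighs more there; the documents do not give the split.

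**Step 4. Chance that any such event arises.** The documents give no rate. Let *p* be the assumed proportion of children with a pre-dose AE that worsens on TAK-536 and is kept as one record. With independent children, P(at least one in 50) = 1 − (1 − *p*)^50.

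| Assumed *p* | P(at least one) |
|---|---|
| 0.5% | 22% |
| 1% | 39% |
| 2% | 64% |
| 5% | 92% |

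The range is wide because *p* is unknown. It does not estimate how many events would be lost.

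**The case against.** The strongest reply is that the worsening bullets already do the work. They have no time limit and no condition on cause, and the switch from placebo to TAK-536 can fairly be read as a change in the study drug. A site that follows them creates a new record dated in the Treatment Period, which is a TEAE under the present definition. A worsening judged related to starting or changing TAK-536 is a new AE on every reading. On this view the missing clause does no harm.

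That stands in part: the loss is conditional on the site using the severity rule. But that rule speaks directly to changes in severity, and a site that applies it is following the protocol as written.

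Other safeguards help less than they seem to. The AE page has items for onset after study drug and for treatment emergence (protocol 10.2.1.2), but the SAP definition does not use them. Prompt reporting of special-interest AEs (protocol 10.2.1.3) reaches the sponsor but does not change the SAP tables. If the event ended treatment, SAP 7.3.5 would still show an AE as the reason, with no matching row among TEAEs leading to discontinuation. Standing blood pressure is analysed separately, so hypotension is not judged from AEs alone.

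Three stronger readings are tempting, and the documents do not support them:

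- **That the event vanishes from the report.** It stays in the Run-in or pretreatment table, and in the serious version if serious. What is lost is TEAE status, intensity and on-drug timing.
- **That the follow-up waiver adds to the loss.** Protocol 10.2.1.2 says certain non-serious AEs "need not to be followed-up for the purposes of the protocol", but only those before first exposure to study drug. Study drug includes the Run-in placebo (protocol 8.1.1), so an AE that starts on placebo is outside the waiver. For earlier AEs, waiving follow-up does not cancel the duty to record a worsening.
- **That TEAE incidence falls by several points.** Supposing 10 to 20% of children have an ongoing AE and 1 in 5 of these worsens gives 50 × 0.10 to 0.20 × 1/5 = 1 to 2 children, or 2 to 4 points. Neither rate is in the documents. The product counts every worsening as lost, including those judged related or recorded as new, and assumes that no affected child has another TEAE. Nor do the documents show that dizziness is common when antihypertensives are stopped.

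**Conclusion.** The point holds in a limited form. Protocol 10.1.2 gives opposite instructions, without precedence, for an AE that starts before the first TAK-536 dose and worsens after it. Where the severity rule is applied, the on-drug worsening is absent from every TEAE table, including the intensity, hypotension and renal tables, and appears only as a Run-in or pretreatment event without intensity. The possible error is one-sided.

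Its size is at most 2 points per affected child in a combined-group row of 50. The number of affected children cannot be derived from the documents and may be zero. That TEAE status follows the start date is an inference: both definitions speak of an AE occurring after the dose. The inference is fair, given protocol 10.1.8 and the SAP's time-of-onset categories. The change is worth making because the rule bears on the primary endpoint and costs little to correct.

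**What to change.** 1. **Protocol 10.1.2.** State that when an AE with onset before the first TAK-536 dose increases in severity or becomes serious at any time after that dose, it is recorded as a new AE dated at the worsening, whatever the judged cause.
2. **Protocol 10.1.2.** Limit the single-record, maximum-severity rule to AEs with onset after the first TAK-536 dose. The two rules still overlap for these AEs, but that affects only the number of events, not TEAE status; a sentence on precedence would settle it.
3. **Protocol 13.1.5 and SAP 7.1.1.** Define a TEAE as an AE that starts or worsens after the first dose for the Treatment Period.

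Changing the SAP alone would not be enough, because a single record holds the maximum severity but no date for the worsening. The cost is wording in the protocol or eCRF guide and in the SAP, plus a few more TEAE records. No treatment rule changes.

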10.1.3 SAEs

An SAE is defined as any untoward medical occurrence in a clinical investigation subject who has signed informed consent to participate in a study:

1. Results in DEATH.
2. Is LIFE THREATENING.
 - The term "life threatening" refers to an event in which the subject was at risk of death at the time of the event; it does not refer to an event that hypothetically might have caused death if it were more severe.
3. Requires inpatient HOSPITALIZATION or prolongation of existing hospitalization.
4. Results in persistent or significant DISABILITY/INCAPACITY.
5. Leads to a CONGENITAL ANOMALY/BIRTH DEFECT.
6. Is an IMPORTANT MEDICAL EVENT that satisfies any of the following:
 - May require intervention to prevent items 1 through 5 above.
 - May expose the subject to danger, even though the event is not immediately life threatening or fatal or does not result in hospitalization.
 - Includes any event or synonym described in the Takeda Medically Significant AE List (Table 10.a).

Table 10.a Takeda Medically Significant AE List

Term	
Acute respiratory failure/acute respiratory distress syndrome	Hepatic necrosis
Torsade de pointes / ventricular fibrillation / ventricular tachycardia	Acute liver failure Anaphylactic shock
Malignant hypertension	Acute renal failure
Convulsive seizure	Pulmonary hypertension
Agranulocytosis	Pulmonary fibrosis
Aplastic anemia	Confirmed or suspected endotoxin shock
Toxic epidermal necrolysis/Stevens-Johnson syndrome	Confirmed or suspected transmission of infectious agent by a medicinal product Neuroleptic malignant syndrome / malignant hyperthermia Spontaneous abortion / stillbirth and fetal death

10.1.4 AEs of Special Interest

An AEs of Special Interest (treatment-emergent only, serious or non-serious) is one of scientific and medical concern specific to the compound or program, for which ongoing monitoring and rapid communication by the investigator or subinvestigator to Takeda may be appropriate. Such events may require further investigation in order to characterize and understand them and would be described in protocols and instructions provided for the investigator or subinvestigator as to how and when they should be reported to Takeda.

10.1.5 Severity of AEs

The different categories of severity are characterized as follows:

- Mild: The event is transient and easily tolerated by the subject.
- Moderate: The event causes the subject discomfort and interrupts the subject's usual activities.
- Severe: The event causes considerable interference with the subject's usual activities.

10.1.6 Causality of AEs to Study Drugs

The causality of each AE to study drugs will be assessed using the following categories:

- Related: An AE that follows a reasonable temporal sequence from administration of a drug (including the course after withdrawal of the drug), or for which a causal relationship is at least a reasonable possibility, i.e., the relationship cannot be ruled out, although factors other than the drug, such as underlying diseases, complications, concomitant drugs and concurrent treatments, may also be responsible.
- Not related: An AE that does not follow a reasonable temporal sequence from administration of a drug and/or that can reasonably be explained by other factors, such as underlying diseases, complications, concomitant drugs and concurrent treatments.

10.1.7 Causality of AEs to Study Procedures

The causality of each AE to study procedures will be assessed.

The causality should be assessed as Related if the investigator or subinvestigator considers that there is reasonable possibility that an event is due to a study procedure. Otherwise, the causality should be assessed as Not Related.

10.1.8 Start Date

The start date of the AE is the date that the first signs/symptoms were noted by the subject and/or the investigator or subinvestigator.

10.1.9 End Date

The stop date of the AE is the date at which the subject recovered, the event resolved but with sequelae or the subject died.

10.1.10 Pattern of Adverse Event

Episodic AEs (eg, vomiting) or those which occur repeatedly over a period of consecutive days are intermittent. All other events are continuous.

10.1.11 Action Taken with Study Treatment

- Drug withdrawn – a study drug is stopped due to the particular AE.
- Dose not changed – the particular AE did not require stopping a study drug.
- Unknown – only to be used if it has not been possible to determine what action has been taken.
- Not Applicable – a study drug was stopped for a reason other than the particular AE eg, the study has been terminated, the subject died, dosing with study drug was already stopped before the onset of the AE, the AE that occurred before the study drug administration.
- Dose Reduced – the dose was reduced due to the particular AE.
- Dose Increased – the dose was increased due to the particular AE.
- Drug Interrupted – the dose was interrupted due to the particular AE.

10.1.12 Outcome

- Recovered/Resolved – Subject returned to first assessment status with respect to the AE.
- Recovering/Resolving – the intensity is lowered by one or more stages: the diagnosis or signs/symptoms has almost disappeared; the abnormal laboratory value improved, but has not returned to the normal range or to baseline; the subject died from a cause other than the particular AE with the condition remaining “recovering/resolving”.
- Not recovered/not resolved – there is no change in the diagnosis, signs or symptoms; the intensity of the diagnosis, signs/symptoms or laboratory value on the last day of the observed

study period has got worse than when it started; is an irreversible congenital anomaly; the subject died from another cause with the particular AE state remaining “Not recovered/not resolved”.

- Recovered/Resolved with sequelae – the subject recovered from an acute AE but was left with permanent/significant impairment (eg, recovered from a cardiovascular accident but with some persisting paresis).
- Fatal – the AEs which are considered as the cause of death.
- Unknown – the course of the AE cannot be followed up due to hospital change or residence change at the end of the subject’s participation in the study.

10.2 Procedures

10.2.1 Collection and Reporting of AEs

10.2.1.1 AE Collection Period

Collection of AEs will commence from the time the subject signs the informed consent. Routine collection of AEs will continue until the end of the Follow-up Period (or the tests performed at early termination).

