When the antihypertensive drugs are required dose reduction or interruption because of the concerns in tolerability with titration (i.e., excessive reduction in blood pressure, other AE, etc.) in the Treatment Period II, the antihypertensive drugs other than TAK-536 (in case of concomitant use) should be reduced or interrupted first. Thereafter, dose reduction or interruption of TAK-536 should be considered.

[figure not shown]
(4) Follow-up Period

Follow-up Period will be 2 weeks from the next day of the final dose of TAK-536. Safety will be evaluated at Week 54 after the start of the Treatment Period.

At the time when the data from approximately 25 subjects are collected, the data until Week 12 in the Treatment Period will be analyzed. In addition, at the time when all subjects complete Week 24 in the Treatment Period, the data until Week 24 in the Treatment Period will be analyzed separately after being locked. These analyses will not intend to continue or discontinue this study.

A schematic of the study design is included as Figure 6.a. A schedule of assessments is listed in Appendix A.

Figure 6.a Schematic of Study Design

- 1) The subjects whose blood pressures meet the inclusion criteria 1 (at earliest) week after receiving placebo in the Run-in Period can enter the Treatment Period. For the subjects only who treated with any antihypertensive drugs as a prior treatment only, the Run-in Period could be extended up to 4 weeks if blood pressures do not meet the inclusion criteria.
 - 2) If subjects have difficulty in discontinuing antihypertensive drugs completely at the start of the Run-in Period, the antihypertensive drugs can be down-titrated concurrently with administration of placebo. In the case of the down-titration, antihypertensive drugs should be discontinued at least 1 week (7 days) before the start of the Treatment Period I. Especially, beta-blockers (BBs) should be tapered off gradually since sudden discontinuation of BBs may cause withdrawal syndrome.
 - 3) In the Treatment Period I, TAK-536 can be titrated biweekly when the subjects do not achieve the target blood pressure while evaluation of safety and tolerability. TAK-536 can be reduced at the investigator's or subinvestigator's discretion if there are any concerns in tolerability with titration of TAK-536 (i.e., in case of occurring any AEs caused by titration of TAK-536).

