9.3.5 Final Visit or Early Termination

The Final Visit will be performed on Week 52 or at the Early Termination Visit.

The tests and observations specified for each visit will be performed.

For subjects early terminate the study after the start of the Treatment Period, if possible, the same tests, observations, and evaluations as those scheduled at Week 52 should be performed.

Whenever possible, office sitting blood pressure should be determined within 3 days after early termination and the other tests, observations, and evaluations should be performed within 14 days after early termination (the next day of the final dose should be calculated as the first day).

For all subjects who entered the Treatment Period, the investigator or subinvestigator must complete the Subject Status on eCRF page with the first day when the subjects received the study drug for the Treatment Period and study completion or early termination status until Week 24 and study completion status at Week 52 for subjects who continuingly received the study drug beyond Week 24.

9.3.6 Follow-up Period: Week 54

Follow-up Period will begin the first day after the final administration of TAK-536 for the Treatment Period and will continue until 2 weeks. The tests and observations specified for each visit will be performed. If subjects terminate the study drug in the Run-in Period or at an early stage of the Treatment Period, no tests, observations, and evaluations will be required but care should be taken for subject safety.

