9.2 Criteria for Markedly Abnormal Values

For each test item, MAV will be determined according to the table below for evaluable data (i.e., non-missing data) obtained within 14 days after the last study drug administration for the Treatment Period (including Day 14 after the last study drug administration for the Treatment Period; the day after the last study drug administration for the Treatment Period to be defined as Day 1). The lower limit of the normal range and the upper limit of the normal range of each test item are abbreviated as LLN and ULN in the table below.

Table 9.c MAV Criteria for Serum Chemistry

Test Item	Gender	Age (years)	MAV Criteria	
			Lower	Upper
BUN (mg/dL)	-	-	-	> 30
Chloride (mEq/L)	-	-	< 75	> 126
Creatinine (mg/dL)	-	-	-	> 2.0
Potassium (mEq/L)			< 3.0	> 6.0
Sodium (mEq/L)			< 130	> 150
eGFR (mL/min/1.73 m ²)			< 30	
ALT (IU/L)	-	-	-	> 3 × ULN
AST (IU/L)	-	-	-	> 3 × ULN
GGT (IU/L)	-	-	-	> 3 × ULN
Total bilirubin (mg/dL)	-	-	-	> 2.0
Creatinine kinase (U/L)				> 5×ULN

Classifying Subjects for the Overall Treatment Period

For each test item and subject, MAV will be determined according to the conditions [1] to [3] provided below. If there are criteria for "Upper" and "Lower" in the MAV Criteria for the same test item, the determination will be made for each criterion.

- [1] A subject will be classified as those "with MAV" if he/she has at least one data that "meets the MAV Criteria" among the evaluable data obtained after the study drug administration for the Treatment Period.
- [2] A subject will be classified as those "without MAV" if he/she does not meet condition [1] and has at least one data that does "not meet the MAV Criteria" among the evaluable data obtained after the study drug administration for the Treatment Period.
- [3] A subject who does not meet conditions [1] or [2] will be excluded from the analysis of MAV for that item.

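### Routine adverse-event collection can end up to 13 days sooner after the last dose for early terminators than for completers, because it may close at the termination tests

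*Protocol*

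**What the plan says.** **When collection ends.** Protocol 10.2.1.1 starts AE collection at consent and then states: "Routine collection of AEs will continue until the end of the Follow-up Period (or the tests performed at early termination").

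**What the Follow-up Period is.** Protocol 6.1: "Follow-up Period will be 2 weeks from the next day of the final dose of TAK-536", with safety evaluated at Week 54. Section 6.2 gives its purpose (safety after dosing) and its length, justified as at least five elimination half-lives, with 12.8 hours observed in healthy adults. Section 9.3.6 defines it in the same way: "Follow-up Period will begin the first day after the final administration of TAK-536 for the Treatment Period and will continue until 2 weeks".

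**When the termination tests happen.** Under 9.3.5 early terminators should have the Week 52 assessments if possible. For timing, "office sitting blood pressure should be determined within 3 days after early termination", and the remaining assessments "should be performed within 14 days after early termination (the next day of the final dose should be calculated as the first day"). A latest day is given, but no earliest day.

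**An exemption.** Section 9.3.6 adds that for a child who stops during the Run-in or "at an early stage of the Treatment Period, no tests, observations, and evaluations will be required". The early stage is not defined.

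**Other capture.** AEs of special interest (hypotension-related and renal) are reportable if they occur in the Follow-up Period (10.2.1.3). AEs arising after first exposure are monitored until they settle or are explained (10.2.1.2). Renal and liver discontinuations have their own follow-up (7.5, 9.1.9). Once the collection period is over, 10.2.2 asks only for serious AEs that are spontaneously reported and considered related to study participation.

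**Analysis.** SAP 7.1.1 defines a treatment-emergent AE (TEAE) by its start only, with no end after the last dose. SAP 7.11.1.2 divides the main TEAE percentages by the whole safety analysis set.

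**The concern.** AEs are the first-listed primary endpoint (Protocol 5.2.1), and the Follow-up Period exists to see what happens after dosing. Read literally, 10.2.1.1 gives two stopping rules: a fixed 2 weeks for completers, and whatever day the tests fall on for early terminators. Because sitting blood pressure is wanted within 3 days, a single visit on Day 1, 2 or 3 is a natural way to comply, and collection could close there.

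A new non-serious event after that visit then has no clear route into the database. Nor does a new serious event that nobody volunteers. The analysis cannot put this right. The main percentages take no account of how long each child was observed. The by-interval table does use an at-risk denominator, but it is built from drug exposure or the occurrence of a TEAE, not from the time during which AEs were being asked about. What is at stake is whether AE ascertainment after the last dose is the same in children who stop and children who finish.

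**Working it through.** **1. The plan's own basis for follow-up.** Inputs: half-life 12.8 h and a 2-week period (Protocol 6.2).

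- 5 half-lives: 5 × 12.8 = 64 h = 2.67 days.
- 2 weeks: 14 × 24 / 12.8 = 26.25 half-lives.

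The stated basis (at least 5 half-lives) reproduces.

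**2. Observation lost, by day of the termination tests.** Days lost = 14 − k, where k is the test day and Day 1 is the day after the last dose (9.3.5). Half-lives elapsed = 24k / 12.8. Fraction of drug remaining = 0.5^(24k / 12.8).

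| Test day k | Days lost | Share of 14 days | Half-lives elapsed | Drug remaining |
|---|---|---|---|---|
| 1 | 13 | 93% | 1.9 | 27% |
| 2 | 12 | 86% | 3.75 | 7% |
| 3 | 11 | 79% | 5.6 | 2% |
| 7 | 7 | 50% | 13.1 | about 0.01% |
| 14 | 0 | 0% | 26.25 | negligible |

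Tests on Day 1 or Day 2 comply with 9.3.5 but fall short of 5 half-lives (adult data).

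**3. Size across the trial.** The documents give no discontinuation rate. Assume that m = 5 to 10 of the 50 stop early, and take the worst case of Day 1 tests for all of them.

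- Child-days lost: 13 × 5 = 65 to 13 × 10 = 130.
- Total AE observation from first TAK-536 dose: (50 − m) × (364 + 14) + m × (s + 14), where s is days on drug before stopping.
- With s = 84 and m = 5: 45 × 378 + 5 × 98 = 17,500, and 65 / 17,500 = 0.37%.
- With s = 84 and m = 10: 40 × 378 + 10 × 98 = 16,100, and 130 / 16,100 = 0.81%.
- Over s = 28 to 168 the range is 0.36% to 0.84%.
- As a share of planned off-drug follow-up (50 × 14 = 700 days): 9.3% to 18.6%.

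If 15 stopped early, the loss would be 195 child-days, or 1.2% to 1.4% of all observation. If the tests all fell on Day 14, the loss would be zero.

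**4. Events.** No AE rate is given either. Assume a probability r of 5% to 40% that a child has a new AE in 14 days, at a constant rate. The expected number of children with a new onset in the 13 lost days is m × [1 − (1 − r)^(13/14)]. This runs from 0.23 (m = 5, r = 5%) to 3.8 (m = 10, r = 40%). Some of these children would already be counted as having a TEAE.

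**5. Can other passages close the gap?** Section 9.3.6 counts the Follow-up Period from the final dose, so an early terminator outside the exemption could be said to have one. Section 10.2.1.3 makes special-interest AEs reportable in that period. Neither requires a contact after the termination tests, and the parenthesis in 10.2.1.1 names those tests as an alternative end of collection. The three sections can be read in two ways.

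**The case against.** The best counter-argument is that 9.3.6 exempts only early-stage stoppers from the follow-up tests. By implication later stoppers keep a 2-week Follow-up Period, and the parenthesis in 10.2.1.1 need not apply to them. The schedule of procedures (Appendix A) is redacted in the public version, so a planned follow-up contact for these children cannot be ruled out. This stands as a possible reading, but it is not written down, and 10.2.1.1 points the other way.

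Second, much is already covered. Existing AEs are monitored to resolution, renal and liver stops are followed, special-interest AEs are reportable in the Follow-up Period, and related serious AEs can still be reported later. This also stands, and it limits the gap to new onsets, mainly non-serious or not volunteered.

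Third, measured against 5 half-lives a Day 1 visit is short by only 64 − 24 = 40 hours, so most of the 13 days lie beyond the pharmacokinetic rationale. That is correct. The inequality with completers remains, since the protocol chose 2 weeks for them.

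A reader might also infer that early stoppers get no follow-up at all. The documents do not say so: the exemption is limited to an undefined early stage, and termination tests are still asked for where possible. Nor do they show that children stop mostly for hypotension or renal change, or are the likeliest to have later events. Section 7.5 lists reasons for stopping without frequencies.

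**Conclusion.** The point holds as a small, cheaply mended inconsistency in AE ascertainment. Per early terminator the loss is 0 to 13 off-drug days. The 93% figure is the worst case (Day 1 tests), not the expected one. Overall the loss is under 1% of follow-up if 5 to 10 of 50 stop early, which is an assumption, but it falls entirely on children who stop.

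Three stronger readings should be resisted.

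- That the primary endpoint as a whole is under-collected. Laboratory tests, ECG, body measurements and standing vital signs belong to the termination assessments; only the new-onset part of the AE component is affected.
- That one missed child shifts a TEAE rate by 2 points (1/50). This is so only if that child had no earlier TEAE in the same count, because SAP 7.11.1.1 and 7.11.1.2 count each child once overall, per system organ class and per preferred term.
- That SAP 9.2 shows 14 days of observation for everyone because it uses laboratory data "obtained within 14 days after the last study drug administration for the Treatment Period". That is an upper limit on which data are used, not a guarantee that a child is observed for so long.

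Sample size and power are unaffected.

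**What to change.** - **Protocol 10.2.1.1 and 9.3.6:** state that AEs are collected, for every child who took TAK-536, through the later of the termination tests or 14 days after the last dose, with a telephone contact if the tests fall earlier. Align 10.2.1.3 with this wording.
- **Protocol 9.3.6:** define the early stage or remove the term, and say that the exemption from tests does not shorten AE collection.
- **SAP 7.1.1:** give the TEAE definition a matching end after the last dose, using the Follow-up Day already defined in SAP 7.1.2.

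The cost is a few sentences and one telephone contact for a few children. The change concerns data collection only; no dose, test or clinical rule is altered.
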